16.4.7.2 Discovery of novel phenotypes

For discovery of novel phenotypes that are based on trajectories of patient characteristics, we will use two approaches: 1) trajectories-based latent class analysis; and 2) group-based trajectories modelling (or these will be substituted or augmented if comparable or better performing models are identified). Given the computational demands of trajectories-based LCA, we may only perform this modelling on clinical data and protein biomarkers and not on transcriptomics data; if methods for transcriptomic data become feasible they will be considered. The time-dependent LCA will be performed using the procedures and features described in the section above, with the addition of repeated measures to identify novel phenotypes. The group-based trajectories modeling (GBTM) will be performed on the repeated measures of the most important variables identified in the time-dependent latent class analyses, and we will seek overlap between this single variable derived cluster and its corresponding latent class. GBTM, like LCA, is a finite mixture modelling approach, and the rationale for its use to interrogate trajectories of a single variable is that it may be more clinically implementable than a multivariate trajectories LCA. The GBTM trajectory monitoring algorithm computes unique equations of the variable of interest as a function of time, which is used to define a subgroup. Individual patients are then classified into the trajectory subgroups using the equation and how closely their measurements match the function defined by the equation. Depending on the variable of interest in the model, we will adjust the GBTM for the effects of treatments such as corticosteroids.

Both for novel and existing phenotypes, we will leverage the breadth of physiological and biological data to better understand the underlying biology of the phenotypes. We will use differential gene-expression analysis and pathway analyses of RNA-sequencing data to study within group and between group

differences in longitudinal gene-expression patterns. Within groups we will use time as variable stratified by survivorship to further study distinct temporal pathways associated with recovery and death.

Longitudinal models will be fit using mixed-effects models that will include a random effect for individual participants. Similar to Aim 2, we will examine the results of joint longitudinal and time-to-event models to account for various dropout mechanisms.

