16.2.8 Aim 2 Adequacy of sample size

The statistical approaches that will be used in the ultimate analysis will be specified *a priori* in a Statistical Analysis Plan. Here, we provide an assessment of the adequacy of the sample size based on reasonable assumptions, recognizing that the final methods will be highly optimized using rapidly developing methodology.

With continuous traits such as plasma protein or nucleic acid quantification, we will have ample power to test for associations with mortality (estimated 30%), specific organ failure (estimated 10 – 40%), or specific post-ICU health impairment (estimated 30%) with the targeted deep phenotyping sample size of 1000-1500 participants at inpatient timepoints and approximately 600 participants at day 90 (3 months). This sample size will also provide adequate power to test for statistical interaction with APS state or other clinical or biological states such as sex, or race/ethnicity. This sample size will also facilitate the ability to preserve cohort participants in the remaining n=2500 of the APS cohort as a validation set for findings identified in the first n=1500 (as a secondary validation procedure to the cross-validation described in Section 12).

For clustering analyses, prior published experience in critical illness phenotypes has successfully identified between 2 and 4 biologic clusters using sample sizes ranging from n=265 to n=1200.^{14–17} With 1500 we expect adequate power for clustering with up to 150 features (more if dimension reduction is employed) as described in the rationale for the cohort sample size.

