16.4.7 Aim 4 Statistical Analysis

It is recognized that methods for analysis continue to be developed and evaluated. A detailed SAP will be generated before analysis begins, in which we will specify the method considered optimal at the time or, if an optimal method cannot be easily determined, competing methods will be compared. The following sections outlines a general approach that might be expected undertaken for this aim.

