The variables used to perform LCA will be similar to those used in our prior studies and include clinical variables and protein biomarkers. Non-normally distributed data will be log-transformed and continuous variables will be scaled using z-scoring using values specific to the study day. Outcome data and severity scores (e.g., APACHE and SOFA scores) will be excluded from the modelling. We will build a minimum of five models, comprising of 1 to 5 classes respectively. We will use fit statistics and the Vuong-Lo-Mendall-Rubin test to determine the best fitting model in each cohort at each timepoint. Once identified, we will use the highest probability generated by the best fitting model to assign class membership. We will use latent transition modelling to evaluate the temporal stability of the classes at sequential time points. To establish overlap with the baseline molecular phenotypes, we will use the parsimonious classifier models comprising of IL-8, protein C, and serum bicarbonate. We plan to use a probability of ≥ 0.5 to assign molecular phenotypes. We will perform mixed effect modeling assessing for overall group differences in parsimonious model probabilities over time between survivorship groups in each phenotype independently. We will perform unadjusted (main) and confounder-adjusted analysis of probabilities trajectories, to ascertain cluster association with outcomes.

For gene-based existing phenotypes, we will use repeated RNA-sequencing data to classify patients to the various phenotypes (SRS, MARS, etc.). We will use the probabilities of belonging to the phenotypes on each day to model for trajectories and use outcome data to evaluate the prognostic value of the changing probabilities and switching of phenotypes, adjusting the models for treatment such as corticosteroids.

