16.4.8 Aim 4 Adequacy of sample size

While the statistical approaches that will be used in the ultimate analysis will be specified *a priori* in a Statistical Analysis Plan, we provide an assessment of the adequacy of the sample size, recognizing that the final methods will be highly optimized using rapidly developing methodology. For the LCA, one of many potential clustering methods, a sample size of 300-500 observations is generally considered sufficient, and we have shown in the cohort sample size rationale that a sample size of 1500 is sufficient for a cluster analysis with 150 variables or more. In our prior work, we identified well separated classes and demonstrated that the proposed variables in our LCA are high quality. The sample sizes proposed here (n=1500-4000 depending on analysis) for the deeply phenotyped subset, and n=1500 for the mechanically ventilated subset, should be sufficient to interpret fit statistics from the LCA overall, and for each component syndrome of APS. These estimates also include later time points where we anticipate at least 1000-1800 patients having molecular data assayed at Day 6 (depending on the variable), with the sample size expected to be slightly larger in sepsis and pneumonia than for ARDS.²⁻⁷

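### Aim 4 gene expression: time effects stratified by survivorship cannot show that a pathway is distinct to recovery or death without a time-by-survivorship contrast

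*Protocol*

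**What the plan says.** Section 16.4.7.2 of the Protocol describes how the biology of the phenotypes will be studied once they are formed: "Both for novel and existing phenotypes, we will leverage the breadth of physiological and biological data to better understand the underlying biology of the phenotypes". For gene expression it starts from this: "We will use differential gene-expression analysis and pathway analyses of RNA-sequencing data to study within group and between group" differences in longitudinal expression. The next sentence sets the survivorship analysis: "Within groups we will use time as variable stratified by survivorship to further study distinct temporal pathways associated with recovery and death".

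The following paragraph gives the model family: "Longitudinal models will be fit using mixed-effects models that will include a random effect for individual participants". It adds joint longitudinal and time-to-event models, but lists no fixed effects or interactions.

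Section 16.4.7.1 handles survivorship differently for another measure: "We will perform mixed effect modeling assessing for overall group differences in parsimonious model probabilities over time between survivorship groups in each phenotype independently". It also models trajectories of RNA-based phenotype probabilities and relates them to outcome, with adjustment for treatments such as corticosteroids.

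Section 16.4.7 introduces all of this as a general approach: "A detailed SAP will be generated before analysis begins, in which we will specify the method considered optimal at the time".

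**The concern.** The sentence on survivorship states a predictor (time), a structure (stratified by survivorship, inside groups) and an inference (distinct pathways for recovery and for death). The inference does not follow from the structure. Resolving illness, treatment and repeated sampling can move expression in the same way in patients who live and patients who die. That common movement enters the time effect of each stratum in full, so a significant time effect in survivors does not tie a pathway to recovery. Nor does significance in one stratum and not the other show a difference, because the strata differ in size and each test carries its own sampling error.

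The planned comparison between groups does not obviously supply the missing contrast. The paragraph is about phenotypes, and survivorship is a stratifier inside the groups, so the groups are most naturally the phenotypes.

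At stake is the biological reading of the phenotypes. Pathways labelled as recovery or death biology could be carried into later work when the data show only a change common to all patients.

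**Working it through.** The Protocol gives no alpha, power or effect size for this analysis, so there is no figure to reproduce. The calculation below is an illustration.

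**Inputs**
- Patients with molecular data at Day 6: 1,000 to 1,800 (section 16.4.8).
- Mortality: 30% (section 16.2.8, stated for Aim 2). Applying it to Day 6 patients is an assumption; 20% to 40% is also shown.
- Size of one phenotype: section 16.1.8 expects 25-30% of the cohort to be hyperinflammatory. The midpoint, 27.5% of 1,000, is 275. At 70:30 this is about 192 survivors and 83 non-survivors.
- Assumed: two-sided alpha of 0.05 per gene, and a true change d from Day 0 to Day 6, in SDs of the paired change, **identical in survivors and non-survivors**.

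**Formulas**
- Power in a stratum of size n: p = P(|Z + d√n| > 1.96).
- Significant in exactly one stratum: p1(1 − p2) + p2(1 − p1).
- Direct contrast: z = (change1 − change2) / √(1/n1 + 1/n2). Its expected value is zero when the changes are equal, so it rejects 5% of the time.

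**One phenotype, 192 v 83, d = 0.2**
- Survivors: 0.2 × √192 = 2.77, power 0.791.
- Non-survivors: 0.2 × √83 = 1.82, power 0.445.
- Exactly one: 0.791 × 0.555 + 0.445 × 0.209 = 0.439 + 0.093 = 0.532.

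**All Day 6 patients, 700 v 300, d = 0.1**
- Powers 0.754 and 0.410.
- Exactly one: 0.445 (survivors only) + 0.101 (non-survivors only) = 0.546.
- Direct contrast, 20,000 simulated genes: 4.7% flagged.

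**Range**

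| Strata | d (SD) | Survivors only | Non-survivors only | Both | Exactly one |
|---|---|---|---|---|---|
| 192 v 83 | 0.1 | 24% | 11% | 4% | 35% |
| 192 v 83 | 0.2 | 44% | 9% | 35% | 53% |
| 192 v 83 | 0.3 | 22% | 1% | 77% | 23% |
| 700 v 300 | 0.1 | 45% | 10% | 31% | 55% |
| 700 v 300 | 0.2 | 7% | 0% | 93% | 7% |
| 700 v 300 | 0.3 | 0.1% | 0% | 99.9% | 0.1% |
| 1,260 v 540 | 0.1 | 34% | 4% | 61% | 37% |

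With 20-40% mortality and 1,000 to 1,800 patients, d = 0.1 gives 28% to 63% in exactly one stratum. At d = 0.3 both strata are significant in at least 98.9% of cases.

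Unequal strata make the error worse but do not create it. At 50:50 with n = 275 and d = 0.2, power is 0.650 in each stratum, and 2 × 0.650 × 0.350 = 0.455 are significant in exactly one.

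**The case against.** The strongest reply is that this is detail for the statistical analysis plan. Section 16.4.7 offers a general approach, section 12.2 leaves methods to plans filed before each analysis, and the mixed-model sentence does not exclude an interaction. The word *distinct* may itself signal that a comparison is intended. Section 12.2.5 asks that treatments be considered and that noise-data simulations be considered for multi-phase procedures. The analysis is supporting work on mechanism; the Aim 4 primary objective, the prognostic value of trajectory phenotypes, does not rest on it.

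Much of this stands, and it limits the point. A reader might infer that Aim 4 never compares survivorship groups over time. Section 16.4.7.1 does so for classifier probabilities and relates RNA-based phenotype probabilities to outcome. A reader might also infer that shared changes will be reported as recovery or death pathways, or that significance in one stratum only is the decision rule. The Protocol states no such rule, writes out no per-stratum model, and does not say how the strata will be reported. Nor does it make these gene lists its source of treatment targets: section 16.4.9 attaches targetable biology to the novel subphenotypes.

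The magnitude also has limits. Alpha and effect sizes are assumed. The 30% comes from Aim 2, whose primary outcome is 60-day mortality, whereas Aim 4 uses in-hospital mortality. The calculation classes single genes, while the plan also speaks of pathways, and no pathway-level error was computed.

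What the reply does not remove is that section 16.4.7.2 names a method, stratification, and attaches to it a conclusion that stratification alone cannot support. An analysis plan that followed the sentence literally would inherit the gap.

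**Conclusion.** The point holds for longitudinal gene expression only. Section 16.4.7.2 makes survivorship-stratified time effects the route to distinct recovery and death pathways and does not name the time-by-survivorship contrast that this conclusion needs. If followed as written, changes shared by survivors and non-survivors can be labelled specific to one outcome.

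The size depends on the shared change and the stratum sizes. It is large for small to moderate changes inside a phenotype (about 53% at n = 275 and 0.2 SD) and for small changes in the whole Day 6 set (about 55% at n = 1,000 and 0.1 SD), against about 5% with a direct contrast. It is close to nil at 0.3 SD with 1,000 or more patients. These figures rest on the assumed 70:30 split, 5% tests per gene and identical true change. They show what the stratified reading can produce and do not predict the results. The correction is worth making because it is nearly free, but no primary result depends on it.

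**What to change.** In section 16.4.7.2, replace the stratified analysis by a time × survivorship term in the mixed-effects model already planned: within each phenotype, expression on time, survivorship and their product, adjusted for treatments such as corticosteroids, with the participant random effect. Base any claim of distinct temporal pathways, and the ranking used for pathway enrichment, on the interaction term. Show the stratum-specific time effects as description. This brings gene expression into line with the survivorship comparison in section 16.4.7.1.

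The change costs a sentence in Aim 4 and in its analysis plan, and needs no new data. The real cost is power. With 192 v 83 the standard error of the contrast is √(1/192 + 1/83) = 0.131 SD, so a true difference in change of 0.2 SD is detected with about 33% power at two-sided 5%. With 700 v 300 the standard error is 0.069 and the power about 83%. Fewer genes will be declared distinct, and the text should say so.

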16.4.8 Aim 4 Adequacy of sample size

While the statistical approaches that will be used in the ultimate analysis will be specified *a priori* in a Statistical Analysis Plan, we provide an assessment of the adequacy of the sample size, recognizing that the final methods will be highly optimized using rapidly developing methodology. For the LCA, one of many potential clustering methods, a sample size of 300-500 observations is generally considered sufficient, and we have shown in the cohort sample size rationale that a sample size of 1500 is sufficient for a cluster analysis with 150 variables or more. In our prior work, we identified well separated classes and demonstrated that the proposed variables in our LCA are high quality. The sample sizes proposed here (n=1500-4000 depending on analysis) for the deeply phenotyped subset, and n=1500 for the mechanically ventilated subset, should be sufficient to interpret fit statistics from the LCA overall, and for each component syndrome of APS. These estimates also include later time points where we anticipate at least 1000-1800 patients having molecular data assayed at Day 6 (depending on the variable), with the sample size expected to be slightly larger in sepsis and pneumonia than for ARDS.²⁻⁷

16.4.9 Aim 4 Expected Output

The completion of these described study objectives will generate the following expected output:

- Evidence to accept or refute a state change from hyperinflammatory subphenotype to a less inflamed phenotype as a prognostic indicator, which can then be tested as a theragnostic marker in future trials
- Novel biologic subphenotypes that incorporate longitudinal data and more diverse data elements than currently exist, which may yield better tools for prediction of long-term health states
- Novel biologic subphenotypes that may demonstrate unique biology that is both identifiable and pharmacologically targetable

16.5.1 Aim 5 Background and Rationale

Background: Efforts to date to understand clinical heterogeneity in ARDS, pneumonia, and sepsis have focused on biological measurements (e.g., plasma biomarkers and vital signs) obtained at the time of acute illness. Yet chronic and constitutional elements of patient biology are important in APS trajectories, both in acute and long-term outcomes. *Rationale:* By performing granular measurements of patients' comorbidities, exposures, and biophysical constitution, we will determine their relative influence and significance in the heterogeneity of APS conditions. This knowledge will equip us to design and trial tailored therapies, informed by each patient's underlying clinical substrate.

16.5.2 Aim 5 Study Objectives

Primary Objective (Aim 5):

We will assess the association between patients' comorbidities, environmental exposures, and biophysical constitution with membership in both previously described and newly identified phenotypes of ARDS, pneumonia, and sepsis. This approach will allow us to identify the contribution of pre-acute illness factors to the pathophysiology of ARDS, pneumonia, and sepsis. There is no intent to develop novel phenotypes under this aim. We will assess the association between exposure history and clinical syndromes, existing molecular phenotypes (e.g., hypo/hyperinflammatory, SRS classes, MARS classes), and phenotypes newly developed under the other aims of this protocol.

The comorbidities of interest are cancer, diabetes mellitus, and cirrhosis; current state and history of these conditions will be considered. The Functional Comorbidity index will also be assessed for contribution to phenotype assignment.

The environmental exposures of interest are cigarette smoking, alcohol use measured using the AUDIT and via blood phosphatidylethanol (PeTH) concentration, air quality index based on 9-digit zip code of residence, and drug use based on urine toxicology screen.

Measures of biophysical constitution are biological sex, age, and body composition (BMI, CT scan imaging), as well as disability assessed using the WHODAS II, cognition assessed using the IQCODE, and frailty assessed using the Clinical Frailty Score.

Exploratory Objectives (Aim 5):

We will assess whether patients' comorbidities, environmental exposures, and biophysical constitution contribute to short-term and long-term outcomes of ARDS, pneumonia, and sepsis, and whether these factors modify the association between phenotype membership and outcomes. Short-term outcomes

include mortality, hospital length of stay, and ICU length of stay. Long-term outcomes include 3-, 6-, and 12-month assessments of physical, respiratory, cognitive, and mental health status.

16.5.3 Aim 5 Study Population

The study population will be the complete cohort of 4000 hospitalized patients as described in the study protocol.

16.5.4 Aim 5 Study Design

Prospective observational cohort study.

16.5.5 Aim 5 Study Procedures

As detailed in the protocol, for each patient we will use surveys to assess the following:

Biophysical constitution: Comorbidities (Functional Comorbidity Index), disability (WHODAS II), cognition (IQCODE), frailty (Clinical Frailty Score), and obesity (BMI). We will also obtain DICOM images from clinically acquired chest and abdominal CT scans to derive indices of body composition.

Psychosocial factors: Social vulnerability (social vulnerability index), social isolation (NHATS 6-item)

Exposures: Air pollution (AQI), tobacco, alcohol (AUDIT). We will also obtain phosphatidylethanol measurements from plasma specimens to estimate cumulative alcohol consumption.

16.5.6 Aim 5 Data, Images, and Biospecimens Used from the APS Consortium

In addition to the listed surveys, we will collect DICOM images from clinically acquired chest and abdominal CT scans to derive indices of body composition and will measure phosphatidylethanol in plasma to estimate alcohol consumption.

16.5.7 Aim 5 Statistical Analysis

As noted for other aims, analyses will either compare outcomes or characteristics between classes, or will identify *de novo* classes. Following the principles laid out in the protocol, each analysis will be pre-specified in a statistical analysis plan. When an optimal approach is not clear, different methods will be compared; comparison of different approaches will be a strong contribution to the methods literature. We also note that discordance between methods can identify informative features and help to further interrogate individual approaches for biological meaning. We have offered multiple approaches for identifying *de novo* classes, for example in Aims 1, 3 and 6. We will follow one of these approaches (or another approach that is considered optimal at the time), replacing the data used in that aim with patient comorbidity, exposure, and biophysical constitution related features.

16.5.8 Aim 5 Adequacy of sample size

Aim 5 includes all 4000 participants. As described in the rationale for the cohort size, this is sufficient for both supervised (e.g., outcome prediction) and unsupervised (e.g. clustering) considering 500 features of

more. Also, when $n=4000$ it is possible to estimate odds ratios of about 0.8 or 1.2 with the half width of the confidence intervals being 0.1 or smaller. This aim has robust statistical power for understanding the role of comorbidities and biophysical constitution on both APS phenotypes and outcomes from ARDS, pneumonia and sepsis.

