Specifically, for Aim 1a (determine how patient-associated microbiota contribute to the heterogeneity of previously derived LCA-defined phenotypes of ARDS, sepsis, and pneumonia), we anticipate that roughly 25-30% of the cohort will be in the “hyper-inflammatory” phenotype and 70-75% will be in the “hypo-inflammatory” phenotype. With a total sample size of 1500 participants, we should therefore have approximately 450 patients in the hyperinflammatory phenotype, with 50-60% of those being mechanically ventilated. (Sinha LRM 2023) In preliminary analyses of blood and plasma mNGS data from 156 sepsis patients, we identified 44% higher prevalence of mNGS-defined bacteremia in hyper-inflammatory compared to hypo-inflammatory patients (74% vs 30%; $p < 0.001$), reflecting the large magnitude of effect sizes that might be observed. As noted in the rationale for cohort sample size, for this ratio of group sizes, a sample size of just 400, and a modest effect (odds ratio of 0.5), the half width of the confidence interval is about 0.25. If the group size is 1500, the half width of the odds ratio is 0.13, assuming a 50% effect rate. Analyses involving all 4,000 persons would result in a half width of 0.08, demonstrating an ability to estimate even small effects with precision. This suggests that the sample is

sufficient to detect meaningful differences in pathogens and microbiota between hyper and hypo classes both within and across the two LCA-defined phenotypes.

Aim 1b (Determine how patient-associated microbiota inform the heterogeneity of ARDS, sepsis, and pneumonia using unsupervised analyses) will follow the approaches to cluster analysis as laid out in the main protocol. We anticipate that at least 500 features can be evaluated for the purposes of unsupervised (or supervised) analyses. The number of features can increase with employment of data reduction techniques.

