16.7.8 Aim 7 Adequacy of sample size

As indicated in the master protocol, there is no clear method for establishing precise sample sizes for unsupervised analyses such as clustering. We have shown in the rationale for the cohort sample size that group sizes of 2000 or more sufficient for identifying clusters when using 500 features or more. For comparison among phenotypes, we have shown that a small effect such as an odds ratio of 0.8 can be estimated with a half width of the confidence interval ranging from about 0.1 to 0.2 under the full range of assumptions.

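### Aim 5's CI half-width of 0.1 or smaller is a best case for OR 0.8 and out of reach for OR 1.2 when the exposure is binary; separately, 16.5.7 commits to class discovery that 16.5.2 rules out

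*Protocol*

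**What the plan says.** On precision, section 16.5.8 states that "Aim 5 includes all 4000 participants" and that at this size "it is possible to estimate odds ratios of about 0.8 or 1.2 with the half width of the confidence intervals being 0.1 or smaller". It closes by calling the power for comorbidities and biophysical constitution robust. For its basis it points to a rationale for the cohort size that is not in the text available here. Section 16.7.8, for an aim that also uses all 4,000 patients, gives for an odds ratio of 0.8 a "half width of the confidence interval ranging from about 0.1 to 0.2 under the full range of assumptions".

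Section 16.1.8 shows how such half-widths are presented elsewhere in the protocol. It says "we anticipate that roughly 25-30% of the cohort will be in the" hyper-inflammatory phenotype. For that ratio of group sizes it gives "a sample size of just 400, and a modest effect (odds ratio of 0.5), the half width of the confidence interval is about 0.25", then "If the group size is 1500, the half width of the odds ratio is 0.13, assuming a 50% effect rate", and finally 0.08 for all 4,000.

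On method, the objective in 16.5.2 is to relate comorbidities, exposures and constitution to membership in existing phenotypes or in phenotypes developed under other aims. It adds: "There is no intent to develop novel phenotypes under this aim". Section 16.5.7 opens by saying that analyses will compare classes or identify new ones. It then cites the de novo class methods of Aims 1, 3 and 6 and ends by committing to one of them (or another method judged optimal at the time), "replacing the data used in that aim with patient comorbidity, exposure, and biophysical constitution related features". Section 16.5.8 also sizes the aim for clustering.

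**The concern.** A half-width on the odds ratio scale grows roughly in proportion to the odds ratio, so one bound for both 0.8 and 1.2 is already doubtful. Section 16.5.8 gives 0.1 as an upper limit, while 16.7.8 gives it as the lower end of a range for the same odds ratio. Three of Aim 5's named factors (cancer, diabetes, cirrhosis) are yes/no conditions, and the known phenotype split is uneven; both widen the interval. If the real half-width is nearer 0.2, an estimate of 0.8 or 1.2 need not exclude 1, and the assurance of robust power does not carry over to those comorbidities.

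The method text raises a different problem. An analyst who follows the last sentence of 16.5.7 would cluster patients on the exposures, which is not the association that 16.5.2 asks for.

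**Working it through.** **Inputs.** n = 4,000, OR 0.8 and 1.2, stated half-width 0.1 or smaller (16.5.8); phenotype share 25-30% (16.1.8). *Assumptions not in the documents:* a 95% level (90% also tried), a two-group contrast without covariates, and any comorbidity prevalence.

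**Formula, binary exposure.** SE(log OR) = sqrt[1/(n1·p1·q1) + 1/(n0·p0·q0)]; half-width = OR·sinh(1.96·SE), which is half the distance between the two limits on the odds ratio scale. The odds ratio is symmetric, so the split and the rate can be read either way round: phenotype share and exposure prevalence, or the reverse.

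**Does this formula match the protocol's own figures?** With OR 0.5, 25-30% in the smaller group and a 50% rate:

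| n | Stated in 16.1.8 | Computed |
|---|---|---|
| 400 | about 0.25 | 0.23-0.25 |
| 1,500 | 0.13 | 0.11-0.12 |
| 4,000 | 0.08 | 0.07-0.075 |

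The match is close, and the stated figures are slightly wider. They behave like 95% half-widths on the odds ratio scale.

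**Best case at n = 4,000** (2,000 per group, 50% overall rate).
- OR 0.8: p = 0.472 and 0.528, p·q = 0.2492 in each group. SE = sqrt(2/(2,000 × 0.2492)) = 0.0633. Half-width = 0.8 × sinh(0.1241) = 0.0996.
- OR 1.2: SE = 0.0633. Half-width = 1.2 × sinh(0.1241) = 0.149.

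A grid over splits and rates from 5% to 95% finds nothing smaller than 0.0996 and 0.149. At 90% confidence the OR 1.2 minimum is still 0.125. Reaching 0.1 at OR 1.2 would take about 4,000 × (0.149/0.1)², or some 8,900 patients, in the balanced case.

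**Less balanced cases, n = 4,000, 95%:**

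| Smaller group | Rate | OR 0.8 | OR 1.2 |
|---|---|---|---|
| 50% | 50% | 0.100 | 0.149 |
| 50% | 30% | 0.109 | 0.163 |
| 30% | 50% | 0.109 | 0.163 |
| 25% | 50% | 0.115 | 0.173 |
| 30% | 30% | 0.121 | 0.175 |
| 25% | 30% | 0.129 | 0.185 |
| 10% (assumed) | 30% | 0.189 | 0.266 |

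In the last row the interval for OR 0.8 is about 0.63 to 1.01, and for OR 1.2 about 0.96 to 1.49. Both include 1.

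**Cross-check from 16.1.8.** Scaling its 0.08 at OR 0.5 in proportion to the odds ratio gives 0.08 × 0.8/0.5 = 0.128 and 0.08 × 1.2/0.5 = 0.192. Neither is 0.1 or smaller.

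**Continuous predictor, per SD.** SE = 1/sqrt(n·p·q), with no correlation with other covariates. At a 50% outcome share, SE = 1/sqrt(1,000) = 0.0316, giving 0.050 (OR 0.8) and 0.074 (OR 1.2). At 25%, SE = 1/sqrt(750) = 0.0365, giving 0.057 and 0.086. Both odds ratios meet 0.1. At a 10% outcome share OR 1.2 gives 0.124, so even this reading depends on the share.

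**Method text.** No arithmetic applies. Section 16.5.2 rules out developing phenotypes under this aim; the close of 16.5.7 says a de novo class method will be run on this aim's own features. Both cannot stand.

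**The case against.** The best defence on precision is that 16.5.8 speaks of what is possible for odds ratios of about 0.8 or 1.2, and that many Aim 5 factors are continuous or scaled: age, BMI, CT body composition, phosphatidylethanol, air quality, the disability and cognition scores. Per SD, the figure holds at outcome shares of 25-50%. Aim 3 (16.3.8) already expresses an odds ratio per standardised unit, and the cohort-size rationale, not available here, may state such a scale. This stands. A reader might infer that 0.1 cannot be reached at all with 4,000 patients; the numbers do not support that. OR 0.8 just reaches it at the balanced optimum, and continuous factors reach it for both odds ratios. What the defence does not rescue is OR 1.2 with a binary exposure, and 16.5.8 extends its assurance to comorbidities without naming a scale.

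The range in 16.7.8 covers varied assumptions, its sentence gives no n, and the sentence before it mentions groups of 2,000 or more. So the two sections are inconsistent in presentation; the clash alone does not prove an arithmetic error. The 10% prevalence above is illustrative only.

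On method, a reader might infer that 16.5.7 leaves the primary association unestimated. That goes too far: its opening clause allows comparison between classes, it permits another approach, and it defers to a pre-specified SAP.

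**Conclusion.** The point holds in a limited form. Under a 95% interval and a binary exposure, the stated bound is a best case for OR 0.8 (0.0996) and unattainable for OR 1.2 (at least 0.149). At a 25-30% smaller group and a 30-50% rate the half-widths are about 0.11-0.13 and 0.16-0.19, roughly 10-30% and 60-90% above the stated 0.1. The bound is met for both odds ratios only per SD of a continuous factor (about 0.05-0.06 and 0.07-0.09 at a 25-50% outcome share, no covariate correlation), and 16.5.8 does not say that this is meant. The confidence level, the absence of covariates and any comorbidity prevalence are assumptions.

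The conflict between the last sentence of 16.5.7 and 16.5.2 is a plain textual one and needs no assumption. Neither part shows that 4,000 is too few for the aim; they show that the stated precision and one sentence of method need correcting.

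**What to change.** In 16.5.8, state the precision by predictor type, with the confidence level, split and rate:
- Binary exposure: about 0.10-0.13 for OR 0.8 and 0.15-0.19 for OR 1.2 when the smaller group is 25-50% and the rate 30-50%.
- Rarer comorbidities: wider, for example about 0.19 and 0.27 at an assumed 10% prevalence and 30% rate.
- Continuous factor: 0.1 or smaller per SD, with the outcome share given.

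Limit the robust-power statement to match, and reconcile the figure with 16.7.8, giving the n and assumptions there too.

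In 16.5.7, replace the closing de novo class sentence with a regression of phenotype membership on the listed pre-illness factors, carrying uncertainty in membership forward as 12.2.5 asks. The exact model can be left to the SAP. The clustering remark in 16.5.8 should then be removed or tied to the aims that do derive phenotypes.

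The cost is wording only. Enrolment and data collection do not change; the stated precision becomes less favourable.
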